## STUDY SYNOPSIS

Study Title: P03277 Dose Finding Study in Central Nervous System (CNS) Magnetic Resonance Imaging (MRI) Phase IIb Clinical Study	
Study Product(s): P03277 [REDACTED]	Active Ingredient(s): P03277
EudraCT No.: 2014-003576-23	IND No.: 123673
	Participating countries (Number of sites): Worldwide study involving approximately 40 centers
Study Objectives	
Primary objective: To determine a safe and effective dose of P03277 based on the Contrast to Noise Ratio (CNR) when comparing with Gadobenate Dimeglumine (MultiHance®) at 0.1 mmol/kg body weight (BW).	
Secondary objectives: 
 
1. To assess technical adequacy of images
 
2. To evaluate capacity of lesion detection
 
3. To evaluate diagnostic information using lesion visualization variables (lesion border delineation, internal morphology and degree of contrast enhancement)
 
4. To evaluate diagnostic confidence
 
5. To compare overall diagnostic preference between P03277 and MultiHance®
 
6. To assess P03277 dose / response relationship for CNR and lesion visualization variables
 
7. To evaluate the impact of P03277 and MultiHance®-enhanced MRI on subject treatment plan
 
8. To assess the safety profile of P03277 as compared to MultiHance® after intravenous administration
 
	
Study design and methodology	
Multi-center, double-blind, randomized, controlled, parallel dose groups, cross-over design with comparator.	
The Investigational Medicinal Products used during the study are P03277 and MultiHance®.	
Two subsets of subjects will be included in the study:	

 
➤ The first subset will include the first subject of each study center. Subjects will be administered at 0.05 or 0.1 mmol/kg BW of P03277 and MultiHance®, 0.1 mmol/kg BW. Images from this subset of subjects will be used to provide training images for the independent blinded off-site readers, to ensure that the imaging protocol/acquisition sequences has been appropriately programmed, and that the MR images produced can be transferred to the core laboratory. Consequently, these subjects will not be included in the efficacy analysis but only for the safety assessment.
 
➤ The second subset will be composed of all subjects (except the first one of each site) selected by the sites. Subjects will be administered at 0.025, 0.05, 0.1, 0.2 mmol/kg BW of P03277 and
 
	

 CONFIDENTIAL	Protocol No. GDX-44-004 Version No. 2.0 (Protocol including amendment n°1) Date: 11 July , 2016	[REDACTED] Page 3 / 84
----------------------------------------------------------------------------------------------------------	----------------------------------------------------------------------------------------------------------	---------------------------

0.1 mmol/kg BW of MultiHance®.

The subjects will be randomly assigned to one of the doses of P03277 and to one series of 2 MRIs performed each at two study visits separated by a wash out period of 2 days minimum up to 14 days. The series are related to the use of contrast agent: one series will have P03277 at visit 2 and MultiHance® at visit 4 or vice versa for the other series.

The randomization scheme will allocate subjects to the two P03277 treatment arms in a 1:1 ratio for the first subset of subjects and to the four P03277 treatment arms in a 1:1:1:1 ratio for the second subset of subjects. The P03277 will be injected at a rate of 2 mL/second.

The same dose of MultiHance®, 0.1 mmol/kg BW by single IV injection at a rate of 2 mL/second, will be injected to all subjects.

The investigator and the subject will remain blinded to IMPs allocation (nature of the IMPs and order of the IMP injection) as well as the dose of P03277 used. A designated unblinded site staff member will be in charge of preparation and administration of the IMPs.

For the second subset of subjects, randomization will be stratified via IWRS by the following stratification factor: presence of brain metastasis (yes/no). Subjects with brain metastasis will be included at a minimum of 20%. MRI images will be evaluated on-site, by investigators and off-site by 3 independent blinded readers. Contrast to Noise Ratio will be evaluated by 3 independent blinded readers and will serve as primary efficacy results.

To allow exact matching of lesions throughout the different imaging sequences and the two MR examination with P03277 and MultiHance®, an independent radiologist (lesion tracker) will perform lesion tracking based only on the available CNS diagrams, separate from the investigator image and independent blinded reader image evaluations.

The IWRS will be used to record subjects visits and allocate IMPs i.e., screening (visit 1), inclusion/first MRI (visit 2), second MRI (visit 4), safety visits (visit 3 and visit 5) and at any time to record screening failure (prior randomization) and premature study discontinuation (after randomization).

For both subsets of subjects, safety will be assessed using vital signs, 12-lead ECGs, injection site tolerance, clinical laboratory parameters (blood and urine) and by adverse events (AEs) monitoring.

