### 5.3 Condition of Investigational Medicinal Product allocation

#### 5.3.1 *Investigational Product(s) Allocation / Randomization*

At visit 2, the subjects will be randomly assigned to one of the doses of P03277 and to one series of 2 MRIs performed each at two study visits separated by a wash out period of 2 days minimum up to 14 days. One series consists of the use of P03277 as contrast agent at visit 2 and MultiHance® at visit 4. The second series consists of the use of MultiHance® at visit 2 and P03277 at visit 4.

The P03277 dose to be injected to the subjects will be attributed by randomization (according to randomization list) at the time of visit 2 simultaneously with the MRIs order allocation.

The randomization scheme will allocate subjects to the two P03277 treatment arms (0.05 or 0.1 mmol/kg BW) in a 1:1 ratio for the first subset of subjects and to the four P03277 treatment arms (0.025, 0.05, 0.1 or 0.2 mmol/kg BW) in a 1:1:1:1 ratio for the second subset of subjects. The P03277 will be injected at a rate of 2 mL/second.

The same dose of MultiHance®, 0.1 mmol/kg BW by single IV injection at a rate of 2 mL/second, will be injected to all subjects.

The randomization will be done via IWRS with a stratification factor for the subset 2: presence of brain metastasis (yes/no) and performed in blocks to prevent unequal treatment allocation. For the subset 2, subjects with brain metastasis will be included at a minimum of 20% in each dose group of P03277.

The study design and the injection of the IMPs require identifying before the study start, two separate teams in each study site. One will manage the blinded data and another one will be unblinded and will be in charge of the IMPs preparation and administration. The unblinded staff will have to document in a separated subject's file all the unblinded information related to the IMPs and will have to complete a dedicated eCRF pages with restricted access.

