## 8 NUMBER OF SUBJECTS

Based on the hypothesis below, a total of 280 subjects will be enrolled in the study:

- First subset: maximum 40 subjects (depending of the number of participating sites) on the basis of 1 subject per site.
- Second subset: 240 subjects based on the following assumption: the study aims at detecting a minimum of 30% increase of CNR for at least one of the four tested dose of P03277 compared to control arm MultiHance® at dose of 0.1 mmol/kg BW. A sample size of 50 evaluable subjects per group is required to obtain a power of at least 90%, using a t-test of a normal mean difference with a 1-sided significance level of 0.025 (Holm's step-down method in a Multiple Comparisons Design) and a common standard deviation of 3.01. Therefore, a minimum of 50 evaluable subjects per dose group and a minimum of 200 evaluable subjects in total will have to be enrolled in this study.

An evaluable subject is defined as a randomized subject, 2 contrast agents administered, having undergone 2 complete, assessable and interpretable MRI examinations, presenting with at least one enhancing lesion of minimum 5 mm (long axis).

It is anticipated that some of the subjects will not complete both MRI evaluations. To offset this, an additional 10 subjects per group will be added to the 50 required leading to a total of 240 randomized subjects.

The number of non-evaluable subjects will be monitored to assess the necessity for a sample size increase. The decision to increase the sample size will be made by the sponsor when approximately 80% of the planned 240 randomized subjects are enrolled. The actual rate of drop-out subjects will be considered to assess the new number of subjects to be enrolled.

Subjects with brain metastasis will be randomized at a minimum of 20% of the second subset of subjects. Randomization will be stratified within brain metastasis (yes/no) in order to prevent unequal treatment allocation.

 CONFIDENTIAL	Protocol No. GDX-44-004 Version No. 2.0 (Protocol including amendment n°1) Date: 11 July , 2016	 Page 42 / 84
----------------------------------------------------------------------------------------------------------	----------------------------------------------------------------------------------------------------------	-----------------------------------------------------------------------------------------------------

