### 3.4. Adjustment for covariates

The pre CNR measurement for unenhanced lesions (baseline value) will be included as covariate in the statistical models for the primary and supportive analyses of the primary criterion.

The stratification factor (brain metastasis at screening) will not be included as covariate in the statistical models. Indeed, it was judged as having no impact on the primary criterion. However, the analysis of number of lesions will be provided only on the subset of subjects with brain metastasis at screening.

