### 3.11. Examinations of subgroups

- Descriptive analyses of the primary criterion will be performed by center and by magnetic field.
- Descriptive analyses of the number of enhancing lesions (secondary efficacy criterion) will be performed by presence or absence of brain metastasis (stratification factor).

CONFIDENTIAL	FORM	
	STATISTICAL ANALYSIS PLAN N° GDX-44-004	
	VERSION 1.0      DATED: 09JAN2018	Page 17 / 60

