### 5.5.3. Additional analyses of primary criterion

### 5.5.3.1 Dose/Response Relationship

The relationship between doses and CNR will be explored by two modeling approaches on all data observed under P03277. On the contrary to previous analyses, all subjects from the FAS with data under P03277 will be taken into account in the analysis, even if they had no MultiHance® in MRI 2. The following models will be performed considering the dose as a continuous variable:

- The *linear model* whose use is justified by the fact that it is the easiest approach needing no *a priori* knowledge of the pattern of relationship between dose and response.
- The *Emax model*, linear in log-dose, which may also be adequate based on existing data of CNR with P03277.

These analyses will be performed for the 3 off-site readers independently.

The linear model fits the dose/response function  $g(\text{dose})$  according to the following formula:

$g(\text{dose}) = E0 + \delta * \text{dose}$ , where  $E0$  is the response at baseline (i.e., absence of dose) and  $\delta$  is a slope factor.

The SAS® procedure used for these analyses will be the following:

```
proc reg data=XXX;  
  model eval =dose;  
  output out=XXX predicted=xx;  
run;
```

The 4-parameter  $E_{max}$  model fitting the dose/response function  $g(dose)$  according to the following formula will be used:

$$g(\text{dose}) = E_0 + (E_{\text{max}} * \text{dose}^{\lambda}) / (E_{\text{D50}}^{\lambda} + \text{dose}^{\lambda})$$

where  $E_0$  is the response at baseline (i.e., absence of dose),  $E_{\max}$  is the asymptotic maximum dose effect (maximum effect attributable to the contrast agent),  $D_{50}$  is the dose which produces 50% of the maximal effect and  $\lambda$  is a slope factor.

CONFIDENTIAL	FORM	
	STATISTICAL ANALYSIS PLAN N° GDX-44-004	
	VERSION 1.0      DATED: 09JAN2018	Page 33 / 60

The SAS® procedure used for these analyses will be the following:

```

proc nlin data = XXX;
  parms E0 = xxx Emax = xxx ED50 = xxx lambda = xxx;
  /* Initial parameters may be estimated based on study data; in particular, lambda may be retrieved from
     the estimated slope parameter in proc reg above */
  model eval = E0 + (Emax * dose** lambda) / (ED50** lambda + dose** lambda);
  output out=XXX predicted=xx;
run;

```

Results from these models will be displayed in tables containing estimates and in figures:

- Dose on X axis.
- CNR on Y axis.

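### Brain metastasis, the only stratification factor named for subset 2, is left out of the dose-response models and of the planned CNR summaries; the cost is small and the remedy is free

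*Protocol*

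**What the plan says.** The protocol synopsis states: "For the second subset of subjects, randomization will be stratified via IWRS by the following stratification factor: presence of brain metastasis (yes/no". Protocol 5.3.1 repeats this: "The randomization will be done via IWRS with a stratification factor for the subset 2: presence of brain metastasis (yes/no". It adds that "subjects with brain metastasis will be included at a minimum of 20% in each dose group of P03277". Protocol section 8 gives the purpose: "Randomization will be stratified within brain metastasis (yes/no) in order to prevent unequal treatment allocation".

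SAP 3.4 then states: "The stratification factor (brain metastasis at screening) will not be included as covariate in the statistical models". The reason follows: "Indeed, it was judged as having no impact on the primary criterion". No data or source is given.

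For CNR subgroups, SAP 3.11 says: "Descriptive analyses of the primary criterion will be performed by center and by magnetic field". SAP 5.5.2.3 matches this, with summaries by site and by field strength and none by stratum. The factor is used for the number of enhancing lesions, which is described by stratum (SAP 3.11) and modelled in metastasis subjects only (SAP 5.5.4.5).

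The primary model (SAP 5.5.1.3) has agent, period and pre-contrast CNR as fixed effects and a random subject effect. The linear dose-response model (SAP 5.5.3.1) uses P03277 data only and reads "model eval =dose". The Emax model also has dose as its only regressor.

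**The concern.** SAP 3.4 gives one reason for leaving the stratum out of all models, but the models are of two kinds. In the primary model each subject supplies both scans, so a stratum main effect drops out of the P03277 minus MultiHance contrast. In the dose-response models different subjects receive different doses, and nothing cancels. Stratified allocation keeps the doses balanced, so the slope is not biased. Any CNR difference between strata remains in the residual, however, and widens the reported standard error.

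The second gap is descriptive. No planned CNR summary would let a reader check the no-impact judgement, or see whether the gain over MultiHance is similar in subjects with and without metastases. A difference of that second kind would not cancel within subject. SAP 5.5.1.5 selects the dose on benefit/risk across primary and secondary criteria, so the supporting CNR outputs may carry some weight.

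**Working it through.** **1. The plan's own figures.** Protocol section 8 gives 4 × (50 + 10) = 240 randomised subjects, which checks. The 20% floor means 0.20 × 240 = 48 metastasis subjects, or 12 of 60 randomised (10 of 50 evaluable) per dose. The figure of 50 per group cannot be confirmed or refuted because the MultiHance mean CNR is not stated. Working backwards from n = 50, 90% power and SD 3.01 (normal approximation):
- paired, one-sided 0.025: 3.01/√50 × (1.960 + 1.282) = 1.38 CNR units;
- two-sample, first Holm step 0.025/4: 3.01 × √(2/50) × (2.498 + 1.282) = 2.28.

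Exact t calculations give 1.41 and 2.31. This range of about 1.4 to 2.3 is the yardstick in step 4.

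**2. Primary model.** The SAP 5.5.1.3 model was simulated with 50 subjects, 10 of them with metastases, an assumed within-subject correlation of 0.5 and 100 runs. It was fitted with and without the stratum. For stratum differences of 0 to 1.5 SD, the ratio of the standard error without the stratum to that with it was 1.0001 to 1.001. Omission is harmless here.

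**3. Dose-response slope.** Let p be the metastasis share and d the CNR difference between strata in residual SDs. Omitting a balanced stratum raises the residual variance from σ² to σ²[1 + p(1−p)d²], so the reported slope SE is multiplied by √[1 + p(1−p)d²]. With p = 0.2, p(1−p) = 0.16. The simulation used 50 subjects per dose, exact balance, SD 3.01 and 2,000 runs.

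| d (assumed) | Formula | Simulated ratio | Mean SE without stratum | Mean SE with stratum | Empirical SD of slope, stratum omitted |
|---|---|---|---|---|---|
| 0 | √1.00 = 1.000 | 1.000 | 3.165 | 3.165 | 3.195 |
| 0.5 | √1.04 = 1.020 | 1.020 | 3.231 | 3.168 | 3.119 |
| 1 | √1.16 = 1.077 | 1.079 | 3.411 | 3.164 | 3.222 |
| 1.5 | √1.36 = 1.166 | 1.168 | 3.705 | 3.175 | 3.228 |

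The last column hardly moves. Under exact balance the slope estimate is the same with or without the stratum, and only its reported SE grows. The consequence is overstated uncertainty, which is conservative, and not bias. No figure was computed for the Emax model.

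**4. What a by-stratum CNR table could show.** The 95% half-width for the mean within-subject difference is t × 3.01 × √[2(1−ρ)]/√n, taking 3.01 as the SD of a single CNR and ρ as the within-subject correlation (assumed).
- n = 10, ρ = 0.5: 2.262 × 3.01 / √10 = 2.15.
- n = 12, ρ = 0.5: 2.201 × 3.01 / √12 = 1.91.
- For n = 10 and 12: 3.05 and 2.70 at ρ = 0; 1.36 and 1.21 at ρ = 0.8.
- n = 50, ρ = 0.5, for comparison: 0.86.

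At ρ = 0.5 the half-widths for metastasis subjects are about as large as the differences in step 1 that the trial is sized to detect.

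**The case against.** The strongest reply is that nothing in the documents shows that CNR differs by metastasis status. The SAP judges that it does not, and if that is right the widening is zero. This stands. A reader might infer that the dose-response error bars are too wide as a matter of fact. The documents do not support that: it depends on an unknown d, and SAP 5.5.3.1 specifies tables of estimates and fitted curves but no intervals or error bars. The fits are exploratory, and no dose-selection rule uses their standard errors.

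A reader might also infer that the factor is ignored throughout, or that the metastasis subjects' CNR result will go unreported. Neither follows. The lesion-count analyses use the factor. SAP 5.4.2 describes it, individual data are listed, and the SAP's detailed table list is blacked out. What can be said is that the visible text plans no CNR summary by stratum. Nor does any objective promise one, since the stated purpose of stratifying is balanced allocation.

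Finally, four doses, three readers and two strata make 24 intervals, with those in the metastasis stratum wide. That also stands, and it is why the table must be labelled descriptive.

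The reply does not explain why a between-subject model should omit the one factor named for stratifying its randomisation. Nor does the SAP offer evidence for the no-impact judgement or a planned CNR output that would test it.

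**Conclusion.** The point holds as a minor one. The primary test is essentially unaffected. The dose-response fits may report somewhat less precision than they have, without bias. At the 20% floor the slope SE is wider by 0% (d = 0), 2.0% (d = 0.5) or 7.7% (d = 1). These figures assume a stratum balanced across doses and values of d that the documents do not supply. The missing CNR description by stratum is a separate gap that remains even if d is zero. Filling it would inform the reader but, at 10 to 12 metastasis subjects per dose, could not confirm a subgroup effect. Both changes are free improvements: they analyse the trial by the groups it already randomises within.

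**What to change.** 1. SAP 5.5.3.1: add brain metastasis (yes/no) as a factor in the linear model and, where the fit converges, as a shift in E0 in the Emax model.
2. SAP 3.11 and 5.5.2.3: add a descriptive CNR table by stratum, dose and reader, with the within-subject P03277 minus MultiHance difference and its 95% CI. State that at the floor of 10 to 12 metastasis subjects per dose the half-width is about 1.9 to 2.2 CNR units (correlation 0.5 assumed), and that the table cannot confirm a subgroup effect.
3. SAP 3.4: limit the exclusion to the within-subject models, on the ground that a between-subject main effect cancels there.

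The cost is SAP wording, one extra model term and one table per reader. Metastasis status is documented at screening (Protocol 9.1.1) and used by the IWRS, so no new data are needed. The primary test, the Holm procedure and the sample size stay as they are.

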### Number of subjects / sample size

Based on the hypothesis below, a total of 280 subjects will be enrolled in the study:

- First subset: maximum 40 subjects (depending on the number of participating sites) on the basis of 1 subject per site.
- Second subset: 240 subjects based on the following assumption: the study aims at detecting a minimum of 30% increase of CNR for at least one of the four tested dose of P03277 compared to control arm MultiHance® at dose of 0.1 mmol/kg BW. A sample size of 50 evaluable subjects per group is required to obtain a power of at least 90%, using a t-test of a normal mean difference with a 1-sided significance level of 0.025 (Holm's step-down method in a Multiple Comparisons Design) and a common standard deviation of 3.01. Therefore, a minimum of 50 evaluable subjects per dose group and a minimum of 200 evaluable subjects in total will have to be enrolled in this study. It is anticipated that some of the subjects will not complete both MRI evaluations. To offset this, an additional 10 subjects per group will be added to the 50 required, resulting in a total sample size of a minimum of

 CONFIDENTIAL	Protocol No. GDX-44-004 Version No. 2.0 (Protocol including amendment n°1) Date: 11 July , 2016	 Page 4 / 84
----------------------------------------------------------------------------------------------------------	----------------------------------------------------------------------------------------------------------	----------------------------------------------------------------------------------------------------

240. In addition, subjects with brain metastasis will be randomized at a minimum of 20% of the second subset of subjects (a minimum of 20% of subjects with brain metastasis per group of P03277 doses).

## **Eligibility criteria**

### Inclusion criteria:

1. Female or male adult subject (subject having reached legal majority age).
2. Subject presenting, at the time of inclusion, with known or highly suspected focal areas of disrupted Blood Brain Barrier (BBB) (e.g., primary and secondary tumors, focal inflammatory disorders) including at least one expected enhancing lesion of minimum 5 mm (long axis). This lesion must have been detected on a previous imaging procedure (computerized Tomography (CT) or MRI).
3. Subject scheduled for a routine CNS contrast-enhanced MRI examination for clinical reasons and agreeing to have a second contrast-enhanced MRI examination for the purpose of the study.
4. Subject able and willing to participate to the study.
5. Subject having read the information and having provided his/her consent to participate in writing by dating and signing the informed consent prior to any study related procedure being conducted.
6. Subject affiliated to national health insurance according to local regulatory requirements.

To be included in the study, the subject must meet all these inclusion criteria.

